7 DISCONTINUATION OF STUDY DRUG AND PATIENT DISSCONTINUATION/WITHDRAWAL

A patient may stop study drug or withdraw from the study at any time for any reason or may be withdrawn at any time at the discretion of the investigator for safety, behavioral, compliance, or administrative reasons. This is expected to be uncommon.

Reasons for removal from study drug and/or from the study include any of the following:

- Liver injury (see Section 7.1 below)]
- Cardiac changes (see Section 7.2 below)
- Adverse events
- Pregnancy
- Protocol deviation
- If the patient meets an exclusion criterion (either newly developed or not previously recognized) that poses a greater risk to the patient with continued participation
- If, in the investigator's opinion, continuation of the study would be harmful to the patient's well being
- Sponsor decision
- Patient request to discontinue study drug or withdraw consent for study participation
- Death
- Lost to follow-up

At the time of discontinuing from the study, if possible, an E/D visit should be conducted, as shown in the SoA (Table 1 and Table 2). See Table 1 and Table 2 for data to be collected at the time of study discontinuation.

Every effort should be made by the site to follow the patient and maintain scheduled safety visits through the Day 104 visit if at all possible, even for patients who voluntarily withdraw their consent.

If the patient withdraws consent for disclosure of future information, the sponsor may retain and continue to use any data collected before such a withdrawal of consent.

If a patient withdraws from the study, he/she may request destruction of any samples taken and not tested, and the investigator must document this in the site study records.

Protocol TB006AD2102

Protocol Date and Version: 15 Oct 2021; v 3.0

7.1 Liver Injury

Discontinuation of study drug for abnormal liver function should be considered by the investigator when a patient meets one of the conditions outlined in Section 10.3 (Appendix 3) or if the investigator believes that it is in best interest of the patient.

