10.3 Appendix 3: Liver Safety: Suggested Actions and Follow-up Assessments

Phase 1 liver chemistry stopping criteria define liver injury, evaluate liver event etiology, and are considered in dose escalation decisions.

Table 9. Phase 1 Liver Chemistry Stopping Criteria and Follow-up Assessments

Liver Chemistry Stopping Criteria			
ALT-absolute	Alanine aminotransferase (ALT) \geq 3 × upper limit of normal (ULN) If ALT \geq 3 × ULN AND bilirubin \geq 2 × ULN (> 35% direct bilirubin) or international normalized ratio (INR) > 1.5, report as a serious adverse event (SAE) ^{a,b}		
	See additional actions and follow-up assessments below		
	Required Actions and Follow-up Assessments		
Actions		Follow-Up Assessments	
 Report the ev 24 hours Complete the (CRF), and co collection too criteria for an Perform liver assessments Monitor the pabnormalities 	discontinue study drug ent to the sponsor within liver event case report form complete an SAE data il if the event also met the SAE ^b function follow-up catient until liver function test resolve, stabilize, or return ee MONITORING)	 Viral hepatitis serology^c Obtain INR and recheck with each liver chemistry assessment until the transaminases values show downward trend Serum creatine phosphokinase (CPK) and lactate dehydrogenase (LDH) Fractionate bilirubin, if total bilirubin ≥ 2 × ULN Complete blood count with differential to assess eosinophilia Record the appearance or worsening of 	
 MONITORING: If ALT ≥ 3 × ULN AND bilirubin ≥ 2 × ULN or INR > 1.5 Repeat liver function tests (include ALT, aspartate transaminase [AST], alkaline phosphatase, bilirubin and INR) and perform liver function follow-up assessments within 24 hours. Monitor patient twice weekly until liver function test abnormalities resolve, stabilize, or return to baseline. 		 Record the appearance of worsening of clinical symptoms of liver injury, or hypersensitivity, on the AE CRF Record use of concomitant medications (including acetaminophen, herbal remedies, and other over-the-counter medications) on the concomitant medications CRF Record alcohol use on the liver event alcohol intake CRF If ALT ≥ 3 × ULN AND bilirubin ≥ 2 × ULN or INR > 1.5: 	

Protocol TB006AD2102

Protocol Date and Version: 15 Oct 2021; v 3.0

 A specialist or hepatology consultation is recommended.

If ALT \geq 3 × ULN AND bilirubin < 2 × ULN and INR \leq 1.5:

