- Repeat liver function tests (include ALT, AST, alkaline phosphatase, bilirubin and INR) and perform liver function follow-up assessments within 24 to 72 hours
- Monitor patients weekly until liver function abnormalities resolve, stabilize, or return to baseline
- Anti-nuclear antibody, anti-smooth muscle antibody, Type 1 anti-liver kidney microsomal antibodies, and quantitative total immunoglobulin G (IgG) or gamma globulins
- Serum acetaminophen adduct high performance liquid chromatography assay (quantifies potential acetaminophen contribution to liver injury in patients with definite or likely acetaminophen use in the preceding week [James et al, 2009])
- Liver imaging (ultrasound, magnetic resonance, or computerized tomography) and/or liver biopsy to evaluate liver disease; complete liver imaging and/or liver biopsy CRFs
- a Serum bilirubin fractionation should be performed if testing is available. If serum bilirubin fractionation is not immediately available, discontinue study drug if $ALT \ge 3 \times ULN$ and bilirubin $\ge 2 \times ULN$. Additionally, if serum bilirubin fractionation testing is unavailable, **record the absence/presence of detectable urinary bilirubin on dipstick** which is indicative of direct bilirubin elevations suggesting liver injury.
- b All events of ALT ≥ 3 × ULN and bilirubin ≥ 2 × ULN (> 35% direct bilirubin) or ALT ≥ 3 × ULN and INR > 1.5 may indicate severe liver injury (possible 'Hy's Law') and must be reported as an SAE (excluding studies of hepatic impairment or cirrhosis). The INR stated threshold value will not apply to patients receiving anticoagulants.
- c Includes: Hepatitis A immunoglobulin M (IgM) antibody; hepatitis B surface antigen and hepatitis B core antibody; hepatitis C RNA; cytomegalovirus IgM antibody; Epstein-Barr viral capsid antigen IgM antibody (or if unavailable, heterophile antibody or monospot testing); and hepatitis E IgM antibody.

Protocol TB006AD2102

Protocol Date and Version: 15 Oct 2021; v 3.0

A patient who met liver chemistry stopping criteria cannot restart study drug unless all of the following conditions are met:

• TrueBinding Inc. approval is granted (as described below)

- Institutional Review Board/Independent Ethics Committee (IRB/IEC) approval is obtained
- Separate ICF for study drug restart/rechallenge is signed by the patient

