If TrueBinding Inc. approval to restart/rechallenge the patient with study drug **is not granted**, then the patient must permanently discontinue study drug and may continue in the study for protocol-specified follow-up assessments.

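### Section 7.1 leaves stopping study drug for liver injury to the investigator's consideration, Table 9 of Appendix 3 puts it under required actions at ALT ≥ 3 × ULN, and nothing says which governs

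*Protocol*

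**What the plan says.** Section 7 of the protocol lists liver injury among the reasons for removal from study drug or from the study, and refers to Section 7.1. Section 7.1 says: "Discontinuation of study drug for abnormal liver function should be considered by the investigator when a patient meets one of the conditions" given in Appendix 3. It adds that the investigator may also act in the patient's best interest.

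Appendix 3 (Section 10.3) is titled "Liver Safety: Suggested Actions and Follow-up Assessments", but its content is firmer than its title:

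- It opens: "Phase 1 liver chemistry stopping criteria define liver injury, evaluate liver event etiology, and are considered in dose escalation decisions".
- Table 9 sets the stopping criterion at ALT ≥ 3 × ULN. The actions, which include discontinuing study drug, stand under "Required Actions and Follow-up Assessments".
- Footnote a to Table 9 says: "If serum bilirubin fractionation is not immediately available, discontinue study drug if" ALT is ≥ 3 × ULN and bilirubin is ≥ 2 × ULN.
- The text after the table says: "A patient who met liver chemistry stopping criteria cannot restart study drug unless all of the following conditions are met". The conditions are sponsor approval, IRB/IEC approval and a separate signed consent form.
- If the sponsor does not approve, "then the patient must permanently discontinue study drug and may continue in the study for protocol-specified follow-up assessments".

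For liver events not caused by study drug, Section 10.3.2 offers a restart route, which among other things asks for ALT below 3 × ULN.

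**The concern.** Section 7.1 sets no threshold of its own. It points to the Appendix 3 conditions, so the same laboratory result triggers both texts: one asks the investigator to think about stopping, the other puts stopping under required actions. Two of the planned 12 to 15 or so sites could act differently on the same ALT value, each in good faith.

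The two texts also set an awkward incentive. An investigator who stops at ALT ≥ 3 × ULN needs three clearances before another dose. One who considers stopping under Section 7.1 and decides to continue needs none, although that site could later be recorded as deviating from Table 9.

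This is the only criterion that the protocol labels a liver stopping criterion. Section 6.2.1 states that there are no concrete stopping criteria for dose escalation, and the synopsis lists committee oversight for Part 1 only, while 58 of the 76 active patients are in Part 2. The patient-level rule therefore carries more of the weight.

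**Working it through.** The main check is a comparison of texts. The arithmetic only bounds the exposure at stake.

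**Step 1. Same trigger, different instruction**

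| Place | Trigger | Instruction | Force |
|---|---|---|---|
| Section 7.1 | An Appendix 3 condition is met | Investigator considers stopping | Discretionary |
| Appendix 3 title | Same | Actions called suggested | Discretionary |
| Table 9 | ALT ≥ 3 × ULN | Discontinue, under required actions | Mandatory |
| Table 9, footnote a | ALT ≥ 3 × ULN with bilirubin ≥ 2 × ULN, fractionation not at hand | Discontinue | Mandatory |
| Text after Table 9 | Stopping criteria met | No restart without three clearances; permanent stop if the sponsor refuses | Mandatory; presupposes a stop |

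All five are current protocol text, not entries in the amendment history.

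**Step 2. Is there a precedence rule?** None was found in protocol Sections 6.2.1, 7, 8 or 10.1.7, or in the SAP.

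**Step 3. Which reading fits the rest?** A bar on restarting has no object if dosing never had to stop. Section 7.2 shows how the protocol words a mandatory rule: the patient who meets the QTc criterion is to be withdrawn. Beside that, the softer verb in Section 7.1 reads as a real choice, so a site could rely on it.

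**Step 4. Doses at stake.** Infusions are on Days 1, 8, 15, 22 and 29. Scheduled post-dose laboratory tests are on Days 8, 22, 36 and 104 (protocol Tables 1 and 2). Doses remain only after the first two of these four tests. Assume that each day's infusion is given before the central-laboratory result returns.

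- Found on Day 8: Days 15, 22 and 29 remain. 3/5 = 60%; 3 × 1,000 mg = 3,000 of 5,000 mg.
- Found on Day 22: Day 29 remains. 1/5 = 20%; 1,000 mg.

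**Step 5. Patients at stake** (Sections 6.1, 6.4.1 and 6.4.2)

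- Planned: 24 + 116 = 140.
- Saline placebo: 6 + 58 = 64.
- Active: 18 + 58 = 76, of whom 6 + 58 = 64 are at the planned 1,000 mg weekly.

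The documents give no expected rate of ALT ≥ 3 × ULN. Assume 1% to 5%:

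- 76 × 0.01 = 0.76 and 76 × 0.05 = 3.8 active patients.
- If half of the elevations were found on Day 8 or 22 (assumption): 0.38 to 1.9.
- The documents do not give that fraction either. From none to all, the range is 0 to 3.8.

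**The case against.** The strongest point is that the decisive cell of Table 9 cannot be read in full. The start of its first action line is lost in the text available for this review, and the missing words could strengthen or qualify the instruction. This stands as a caveat. For ALT alone, the mandatory reading rests on the table headings and the restart text, not on a complete sentence.

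Footnote a gives limited help. It covers ALT together with bilirubin, and if ALT alone always forced a stop, the footnote would be partly redundant. That also stands: it supports stopping in the combined case and does not settle the case of ALT alone. Likewise, Section 7 lists reasons for removal that plainly do not each force removal, such as adverse events, so liver injury appearing there proves little.

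There are also real safeguards:

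- exclusion at entry of ALT > 1.5 × ULN;
- a report to the sponsor within 24 hours;
- repeat tests within 24 to 72 hours (within 24 hours if bilirubin or INR is also raised);
- weekly or twice-weekly monitoring;
- discussion of immediate safety concerns with the sponsor, who may also decide on removal;
- in Part 1, a safety committee that takes liver enzyme rises into account.

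The monkey toxicology study showed no adverse treatment-related findings. These points lower the likely harm, but none tells a site whether to give the next infusion.

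A site that follows the cross-reference to Appendix 3 will meet the restart rules at once, which narrows the room for misreading. It does not close it, because the appendix title itself calls the actions suggested.

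**Conclusion.** The concern holds. Followed as written, Section 7.1 permits continued dosing that Table 9, on its headings and restart rules, does not. This is an unclear safety rule rather than an absence of oversight, and it should be fixed.

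The exposure at stake is at most 3 further infusions for a patient (60% of the course), and at most about 0.8 to 3.8 of 76 active patients at the assumed 1% to 5% rate. All of these are upper bounds. They assume that the investigator keeps dosing despite sponsor contact and repeat tests, and the rate has no source in the documents. The textual conflict does not depend on these figures. Sample size, power and type I error are unaffected.

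**What to change.** Reword Section 7.1 along these lines: *Study drug must be discontinued when a patient meets the liver chemistry stopping criteria in Appendix 3 (Table 9). The investigator may also discontinue it below these thresholds when that serves the patient.*

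Retitle Appendix 3, and its contents entry, so that the actions are called required instead of suggested. When making the change, the sponsor should confirm that the full first action line of Table 9 agrees with it. If so, Table 9 and the restart text can stay as they are; Section 10.3.2 already provides for transient elevations unrelated to study drug.

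The cost is one sentence and one heading in the next amendment, with no added procedures, visits or samples.

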7.2 Cardiac Changes

A patient who meets the below criteria based on the average of triplicate ECG readings will be withdrawn from the study:

• Change from baseline: sustained QTc > 60 msec

If a clinically significant finding is identified (including, but not limited to changes from baseline in QTcB or QTcF after study drug infusion), the investigator or qualified designee will determine if the patient can continue in the study and if any change in patient management is needed. This review of the ECG printed at the time of collection must be documented. Any new clinically relevant finding should be reported as an AE.

7.3 Lost to Follow up

A patient will be considered lost to follow-up if he or she repeatedly fails to return for scheduled visits and is unable to be contacted by the study site.

The following actions must be taken if a patient fails to return to the clinic for a required study visit:

- The site must attempt to contact the patient and reschedule the missed visit as soon as possible and counsel the patient on the importance of maintaining the assigned visit schedule and ascertain whether or not the patient wishes to and/or should continue in the study.
- Before a patient is deemed lost to follow up, the investigator or designee must make every effort to regain contact with the patient or caregiver (where possible, 3 telephone calls and, if necessary, a certified letter to the patient's last known mailing address or local equivalent methods). These contact attempts should be documented in the patient's medical record.
- Should the patient continue to be unreachable, he/she will be considered to have withdrawn from the study.

Discontinuation of specific sites or of the study as a whole are handled in Section 10.1.8.

Protocol TB006AD2102

Protocol Date and Version: 15 Oct 2021; v 3.0

8 STUDY ASSESSMENTS AND PROCEDURES

• Study procedures and their timing are summarized in the SoA (Table 1 and Table 2). Protocol waivers or exemptions are not allowed. Specifications related to protocol deviations are presented in Section 10.1.7.

- Immediate safety concerns should be discussed with the sponsor immediately upon occurrence or awareness to determine if the patient should continue or discontinue study drug.
- Adherence to the study design requirements, including those specified in the SoA (Table 1 and Table 2), is essential and required for study conduct.
- All screening evaluations must be completed and reviewed to confirm that potential patients meet all eligibility criteria. The investigator will maintain a screening log to record details of all patients screened and to confirm eligibility or record reasons for screening failure, as applicable.
- Procedures conducted as part of the patient's routine clinical management (eg, blood count) and obtained before signing of the ICF may be utilized for screening purposes, provided the procedures met the protocol-specified criteria and were performed within the time frame defined in the SoA (Table 1 and Table 2).
- The maximum amount of blood collected from each patient over the duration of the study, including any extra assessments that may be required, will not exceed 250 mL (see Table 6 and Table 7). Repeat or unscheduled samples may be taken for safety reasons or for technical issues with the samples.

8.1 General Study Periods

8.1.1 Screening, Enrollment and/or Randomization

Screening will occur between Day -28 and Day -2. The purpose of the screening period is to obtain informed consent and to establish protocol eligibility. Informed consent will be obtained after the study has been fully explained to each patient and before the conduct of any screening procedures or assessments. Procedures to be followed when obtaining informed consent are detailed in Section 10.1.3 (Appendix 1).

Screening assessments are performed as outlined in the SoA (Table 1 and Table 2).

8.1.2 Study Drug Administration and Follow-up Period

Following randomization, patients will receive study drug as an IV infusion at qw intervals, for 5 doses. Study assessments will be performed up to Day 104 as outlined in the SoA (Table 1 and Table 2).

8.2 Safety Assessments

Planned time points for all safety assessments are provided in the SoA (Table 1 and Table 2).

Protocol TB006AD2102

Protocol Date and Version: 15 Oct 2021; v 3.0

8.2.1 Physical and Neurological Examinations

• A complete physical examination will include, at a minimum, assessments of the cardiovascular, respiratory, gastrointestinal and neurological systems.

- The neurological examination will assess mental status, motor and sensory skills, hearing and speech, vision, coordination, and balance.
- Height and weight will also be measured and recorded. Height will only be measured at screening.
- Investigators should pay special attention to clinical signs related to previous serious illnesses.

8.2.2 Vital Signs

- Oral temperature, pulse rate, respiratory rate, and blood pressure will be assessed as indicated in the SoA (Table 1 and Table 2).
- Blood pressure and pulse measurements will be assessed with a completely automated device. Manual techniques will be used only if an automated device is not available.
- Blood pressure and pulse measurements should be preceded by at least 5 minutes of rest with the patient in a quiet setting without distractions (eg, television, cell phones). Blood pressure measurements will be taken with the patient in the sitting position.
- Vital signs will be taken before blood collection for laboratory tests, if that is scheduled for the same time point.

8.2.3 Electrocardiograms

- 12-lead ECG measurements will be obtained as outlined in the SoA (Table 1 and Table 2) using an ECG machine that automatically calculates the heart rate and measures PR, QRS, QT, and QTc intervals (triplicate measurements will be obtained at all-time points, except at the screening visit where a single measurement will be obtained). Refer to Section 7.2 for QTc withdrawal criteria and any additional QTc readings that may be necessary.
- At each time point at which triplicate ECG are required, 3 individual ECG tracings should be obtained at 2-minute intervals.
- On non-dosing days, effort should be made to perform 12-lead ECGs time-matched with the pre-dose time point on dosing days.
- The PI or designated site physician will review and assess all ECGs as Normal, Abnormal, or Not Evaluable. Once signed, the original ECG tracing will be retained with the patient's source documents. At the request of the sponsor, a copy of the original ECG will be made available to the sponsor.
- On Part 1 only, ECGs will be transferred electronically to an ECG central reader for analysis according to the study-specific recommendations included in the ECG manual. The central ECG reader will review machine reads and provide corrected values as specified in the manual. The following parameters will be recorded: PR interval, RR interval, QRS complex/duration, QT interval, QTc, heart rate, and clinical interpretation.

Protocol TB006AD2102

Protocol Date and Version: 15 Oct 2021; v 3.0

• The results from the central reader will be captured in the study database, together with the investigator assessment of the ECG.

• In Part 2, only the machine readings and investigator interpretations will be recorded in the study database.

8.2.4 Clinical Safety Laboratory Assessments

- The tests detailed in Table 5 will be performed by the central laboratory; see the SoA (Table 1 and Table 2) for the timing and frequency.
- Protocol-specific requirements for inclusion or exclusion of patients are detailed in Section 5 of the protocol.
- Additional tests may be performed at any time during the study as determined necessary by the investigator or required by local regulations.
- The investigator must review the laboratory report and document this review. The investigator should consider documenting any clinically relevant changes as AEs in the CRF. The laboratory reports must be filed with the source documents. Clinically significant abnormal laboratory findings are those that are not associated with the underlying disease, unless judged by the investigator to be more severe than expected for the patient's condition.
- All laboratory tests with values considered clinically significantly abnormal during participation in the study should be repeated at appropriate intervals until the values return to normal or baseline or are no longer considered clinically significant by the investigator or Medical/Scientific Monitor.
- If such values do not return to normal/baseline within a period of time judged reasonable by the investigator, the etiology should be identified and the sponsor notified.
- All protocol-required laboratory assessments, as defined in this section, must be conducted in accordance with the laboratory manual and the SoA (Table 1 and Table 2).
- If laboratory values from non-protocol specified laboratory assessments performed at the institution's local laboratory require a change in patient management or are considered clinically significant by the investigator (eg, SAE, or AE, or dose modification), then the results must be recorded in the CRF.

Protocol TB006AD2102

Protocol Date and Version: 15 Oct 2021; v 3.0

 Table 5.
 Protocol-required Clinical Safety Laboratory Assessments

Hematology	Clinical Chemistry	Urinalysis
Platelet count	BUN	Specific gravity
RBC count	Creatinine	pH, glucose, protein, blood,
Hemoglobin	CPK	ketones, bilirubin, urobilinogen,
Hematocrit	Glucose (nonfasting)	nitrite, leukocyte esterase by
RBC Indices:	Potassium	dipstick
MCV	Sodium	Microscopic examination (if
MCH	Calcium	blood or protein is abnormal)
%Reticulocytes	AST/SGOT	
WBC count with differential:	ALT/SGPT	
Neutrophils	Alkaline phosphatase	
Lymphocytes	Total and direct bilirubin	
Monocytes	Total protein	
Eosinophils	Albumin	
Basophils	Total cholesterol	
	HDL	
	LDL	
	Triglycerides	
	TSH	
	HbA1c	

Other Screening Tests

Urine alcohol and drug screen (including but not limited to opiates, methadone, buprenorphine, methamphetamine, cocaine, and amphetamines)

Viral serology (HBsAg, IgM anti-HBc, anti-HCV, HIV) and COVID-19

The results of each test must be entered into the CRF.

ALT = alanine aminotransferase; anti-HCV = hepatitis C virus antibody; AST = aspartate aminotransferase; BUN = blood urea nitrogen; COVID = coronavirus disease; CPK = creatine phosphokinase; CRF = case report form; HbA1c = hemoglobin A1c; HBsAg = hepatitis B surface antigen; hCG = human chorionic gonadotropin; HDL = high-density lipoprotein; IgM anti-HBc = immunoglobulin M antibody to hepatitis B core antibody; LDL = low-density lipoprotein; MCH = mean corpuscular hemoglobin; MCV = mean corpuscular volume; RBC = red blood cell; SGOT = Serum Glutamic-Oxaloacetic Transaminase; SGPT = Serum Glutamic-Pyruvic Transaminase; TSH = thyroid-stimulating hormone; WBC = white blood cell.

